#### 7.1.4 EVENT REPORTING FOR DISEASE PROGRESSION OR EXCLUSIONARY HISTOLOGIC FINDINGS POST-STUDY TREATMENT

After starting study treatment, if there is histologic confirmation of progression of HSIL to microinvasive or invasive squamous cell carcinoma, the event must be reported as an SAE. For the finding of carcinoma, subjects should be managed per routine standard of care (i.e. surgical excision), discontinued from study treatment but continue on study without further biopsy. Post-study treatment histologic diagnosis of adenocarcinoma-in-situ or adenocarcinoma should also be reported as an SAE. In both instances the condition for SAE reporting should be categorized as a medically important event unless another criterion is met.

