## 8.4 ANALYSES POPULATIONS

Analysis populations will include:

- The modified intention to treat (mITT) population includes all subjects who receive at least one dose of Study Treatment and who have the analysis endpoint of interest. Subjects in this sample will be grouped to treatment arms as randomized. Analysis of the mITT population will be primary for the analysis of efficacy in this study.
- The per-protocol (PP) population comprises subjects who receive all doses of Study Treatments and have no protocol violations and who have the analysis endpoint of interest. Subjects in this sample will be grouped to treatment arms as randomized. Analyses on the PP population will be considered supportive of the corresponding mITT population for the analysis of efficacy. Subjects excluded from the PP population will be identified and documented prior to unblinding of the study database.
- The safety analysis set includes all subjects who receive at least one does of Study Treatment. Subjects will be analyzed as to the treatment they received.

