## 8.9 EFFICACY ANALYSIS

The true treatment effect on the primary endpoint is  $p$ , where  $p$  denotes the true population probability of the primary endpoint for each arm. The primary hypothesis of superiority is:  $H_0: p \leq 0.02$  vs.  $H_1: p > 0.02$ , for each treatment arm separately.

A p-value for these hypothesis tests and corresponding 95% confidence intervals will be computed based on the method of Clopper-Pearson. Superiority will be concluded if the one-sided p-value is  $< 0.025$  and the corresponding lower bound of the 95% CI exceeds 0.02.

The secondary efficacy binary endpoints will be analyzed in the same manner as the primary hypothesis, but without the hypothesis test p-values.

For the analyses, the efficacy time frame is defined by any time starting from 14 days prior to the -specified visit week.

The anatomic extent endpoint will be analyzed by calculating the mean percent change and associated 95% t-distribution based confidence interval. The percentage of subjects with no clinically significant lesion resolution (reduction in lesion size of 25% or less), partial lesion resolution (26-99% reduction), and complete reduction (100% reduction) will be summarized with point estimates and associated Clopper-Pearson 95% confidence intervals.

An exploratory analysis will examine clearance outside of the vulva. This will be analyzed in the same manner as vulvar clearance.

An exploratory analysis will examine the relationship between the primary efficacy endpoint and HLA results. As these results are categorical, relationships will be examined with contingency tables and logistic regression models which model the primary endpoint versus these results and treatment group as regressor variables.

An exploratory analysis will examine the relationship between the primary efficacy endpoint and needle depth into muscle. A logistic regression model which models the primary endpoint versus these results and treatment group as regressor variables will be used.

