#### 8.11.6 MISSING VALUES

Missing data will not be imputed or replaced, and calculations will be done on reported values.

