## 2.2 SECONDARY OBJECTIVES AND ASSOCIATED ENDPOINTS

Secondary Objectives	Associated Secondary Endpoints
1. Evaluate the safety and tolerability of VGX-3100 delivered IM followed by EP with CELLECTRA® 2000, alone or in combination with imiquimod	1a. Local and systemic events for 7 days following each dose as noted in the Participant Diary. 1b. All adverse events including SAEs, SUSARs, UADEs, and other unexpected AEs for the duration of the study (through Week 100 visit)
2. Determine the efficacy of four doses of VGX-3100, alone or in combination with imiquimod, as measured by histologic regression of vulvar HSIL	2. Proportion of subjects with no evidence of vulvar HSIL on histology (i.e. biopsies or excisional treatment) at Week 48 visit
3. Determine the efficacy of four doses of VGX-3100, alone or in combination with imiquimod, as measured by virologic clearance of HPV-16/18 in vulvar tissue	3. Proportion of subjects with no evidence of HPV-16/18 in vulvar tissue samples at Week 48 visit
4. Determine the efficacy of VGX-3100 , alone or in combination with imiquimod, as measured by histologic regression of vulvar HSIL to normal tissue	4. Proportion of subjects with no evidence of vulvar HSIL and no evidence of condyloma on histology (i.e. biopsies or excisional treatment) at the Week 48 visit
5. Determine the efficacy of four doses of VGX-3100 , alone or in combination with imiquimod, as measured by non-progression of vulvar HSIL to vulvar cancer as determined by histology	5. Proportion of subjects with no progression of vulvar HSIL to vulvar cancer from baseline to Week 48 visit

 No evidence of vulvar HSIL is defined as normal tissue or vulvar LSIL (VIN 1) or condyloma

 Clearance of HPV-16 or HPV-18 is defined as being undetectable by PCR assay.

 Progression is defined as advancement to carcinoma according to the Pathology Adjudication Committee by histology.

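### Secondary endpoint 5 counts cancers over the whole interval from baseline to Week 48, but the one efficacy window in Section 8.9 opens at Week 46 and makes no exception for it

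*Protocol*

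**What the plan says.** Section 2.2 defines endpoint 5 as the proportion with no progression "of vulvar HSIL to vulvar cancer from baseline to Week 48 visit". Its footnote reads: "Progression is defined as advancement to carcinoma according to the Pathology Adjudication Committee by histology". Secondary endpoints 2 to 4 are instead each read at the Week 48 visit.

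Section 8.9 gives one timing rule: "For the analyses, the efficacy time frame is defined by any time starting from 14 days prior to the -specified visit week". It sets an opening and no close, and only the opening matters here. The same section adds: "The secondary efficacy binary endpoints will be analyzed in the same manner as the primary hypothesis, but without the hypothesis test p-values". No endpoint is exempted.

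Tissue can be taken before Week 48. Section 6.14 allows an unscheduled biopsy on suspicion of progression, and Table 13 lists carcinoma among its possible results. Section 3.2 sends any wide-excision sample from a woman with worsening disease to the PAC. After a carcinoma finding, Section 7.1.4 has her "discontinued from study treatment but continue on study without further biopsy".

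On who is analysed, the mITT population in 8.4 "includes all subjects who receive at least one dose of Study Treatment and who have the analysis endpoint of interest". Section 8.11.6 states: "Missing data will not be imputed or replaced, and calculations will be done on reported values".

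The wording of Sections 8.4, 8.9 and 8.11.6 is taken from protocol versions 1.0 and 1.1, which agree. Section 8 of version 1.2 is not in the text available. Its summary of changes lists only the removal of a patient-reported instrument and otherwise administrative changes, so these sections are assumed unchanged. Endpoint 5 is worded identically in versions 1.1 and 1.2.

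**The concern.** A time frame tied to a visit suits an endpoint read at that visit. It does not suit one that accumulates events from baseline, because it admits only what is seen from two weeks before the end of the interval. The events left out would be the early cancers.

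Endpoint 5 is the only efficacy endpoint that isolates progression to cancer. The responder endpoint merges it with persistent HSIL and persistent HPV. Section 1.1.8 names the possible delay in treating vulvar HSIL as the reason for enhanced monitoring, so this proportion speaks directly to that risk. Under the literal rule, the efficacy table could show 100% non-progression while the safety tables list a carcinoma as an SAE.

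The text of Section 3.2.1 above Table 4 makes any histologically confirmed progression a non-response, without a time limit. (Table 4 itself refers only to carcinoma at evaluation.) That rule protects the responder endpoint. Nothing carries it over to endpoint 5.

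**Working it through.** **1. The plan's own figure.** No figure is given for endpoint 5. The only one nearby is the sample size in 8.3, and it reproduces. With an exact binomial test of p = 0.02 at one-sided 0.025, the smallest evaluable numbers with at least 80% power are:
- 21, requiring 3 or more responders (power 82.1% at a true rate of 20%);
- 10, requiring 2 or more responders (power 81.7% at a true rate of 28%).

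Allowing for 90% evaluable, 21/0.9 = 23.3, rounded up to 24, and 10/0.9 = 11.1, rounded up to 12, for a total of 36. The present point does not depend on this result. It uses only the evaluable counts: 24 × 0.9 = 21.6, about 22, and 12 × 0.9 = 10.8, about 11.

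**2. When the window opens.** 48 × 7 − 14 = 322 days, and 322/7 = Week 46.

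**3. One woman with PAC-confirmed carcinoma before Week 46.**
- By the definition in 2.2 she has progressed and is an event.
- By 8.9 read literally, her result predates the time frame.
- By 7.1.4 she has no later biopsy, so no scheduled tissue falls inside the time frame.
- By 8.4 and 8.11.6 she is then without the endpoint and is not imputed, so she leaves the denominator. If she is kept, she has no event inside the window and counts as a non-progressor.

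**4. Effect of one such case.** Assume that she is one of the 22 or 11 and that no other cancer occurs. Clopper-Pearson 95% limits are the Beta(x, n − x + 1) quantile at 0.025 and the Beta(x + 1, n − x) quantile at 0.975. When x = n the lower limit is 0.025^(1/n).

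| Handling | VGX-3100 alone | VGX-3100 + imiquimod |
|---|---|---|
| Counted as progression | 21/22 = 95.5% (77.2 to 99.9) | 10/11 = 90.9% (58.7 to 99.8) |
| Dropped | 21/21 = 100% (83.9 to 100) | 10/10 = 100% (69.2 to 100) |
| Kept as event-free | 22/22 = 100% (84.6 to 100) | 11/11 = 100% (71.5 to 100) |

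The overstatement is 1/22 = 4.5 points or 1/11 = 9.1 points. With two early cancers in an arm, the endpoint as defined gives 20/22 = 90.9% (70.8 to 98.9) or 9/11 = 81.8% (48.2 to 97.7). The literal window still gives 100%.

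**5. How likely a case is.** The protocol gives no cancer rate by Week 46. Purely as an assumption, a per-woman risk of 1% to 5% implies 36 × 0.01 = 0.36 to 36 × 0.05 = 1.8 expected cases. The chance of at least one is 1 − 0.99^36 = 30% to 1 − 0.95^36 = 84%. Section 1.1.8 describes progression as typically taking years, which favours the low end or below. Section 1.1.3 does cite a range starting at 4 months for VIN3, so a case before Week 46 is not excluded.

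**The case against.** The strongest reply is that endpoint 5 carries its own time frame. The 8.9 sentence maps results to a specified visit, which fits endpoints read at a visit, and a specific interval in an endpoint definition would normally prevail over a general window. On that reading a woman with carcinoma at Week 20 has the endpoint of interest: she progressed. Nothing is missing, and no Week 48 tissue is needed. The any-case rule in 3.2.1 suggests that the drafters meant early progression to count. This reading is reasonable, and it stands as a reason not to call the loss of early cancers certain. It does not remove the conflict. No text states that the endpoint's interval prevails, and in an open-label trial that choice should not wait until a case is known.

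The limited consequence also stands. Endpoint 5 has no p-value, and neither the sample size nor a decision rule rests on it. The intervals in the table overlap heavily. An early carcinoma must be reported as an SAE, 8.11.1 includes summaries regardless of timing, and the DSMB reviews safety data.

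Window exceptions are often left to a statistical analysis plan, and one may exist. The point here is narrower: 8.9 does state a rule, and that rule does not fit this endpoint.

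**Conclusion.** The misfit is in the text. A cumulative endpoint sits under a single visit window with no exception, and the literal result is that cancers before Week 46 are dropped or counted as event-free. The size is about 4.5 points per case in the VGX-3100 arm and 9.1 points in the combination arm. This assumes about 22 and 11 evaluable women, a literal reading of 8.9, at least one PAC-confirmed carcinoma before Week 46, and an unchanged Section 8 in version 1.2.

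A reader might infer more: that early cancers are certainly excluded, that most would come to light through unscheduled biopsies, or that cancers would be hidden. The documents do not support these. The endpoint wording allows the other reading, nothing ranks unscheduled biopsy above the scheduled Week 48 biopsy as a source of carcinoma findings, and every case is an SAE. Priority is low to moderate.

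**What to change.** Add to Section 8.9 that the 14-day window does not apply to secondary endpoint 5; that any PAC-confirmed carcinoma from first dose through the Week 48 visit counts as progression, whether the tissue came from a scheduled or an unscheduled biopsy or from excision; and that the woman stays in the denominator of her randomised arm. If a statistical analysis plan exists, repeat it there.

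The cost is a sentence or two. No new data are needed, because the PAC already reviews all biopsy and excision samples, and neither the sample size nor the care of any woman changes.

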## STUDY SCHEDULE OF EVENTS

**Table 1: Schedule of Events**

Tests	Screen (-10 wk to -1d)	Day 0	8-14 days post dose 1 Phone Call	Week 4 (± 7 days)	8-14 days post dose 2 Phone Call	Week 12 (± 7 days)	Week 15 (± 7 days)	Week 24 (± 7 days)	Week 27 (± 7 days)	Week 38 (± 7 days) Phone Call	Week 48 (± 7 days)	Week 52 (± 14 days)	Week 74 (±14 days)	Week 78 (± 14 days)	Week 96 (± 14 days)	Week 100 (± 14 days)
Informed consent	X															
Medical History/Demographics	X															
Medications (prior/concomitant)	X	X							X							
Socio-behavioral assessment	X										X					X
Inclusion/Exclusion criteria	X	X														
Randomization		X														
Physical exam (PE)/assessment a	X	X		X		X		X	X		X	X	X	X	X	X
Vital signs	X b	X		X		X		X	X		X	X	X	X	X	X
Screening safety (12 lead ECG, labs) c	X															
Pregnancy Testing d	X	X		X		X		X	X		X	X	X	X	X	X
HIV Ab by ELISA	X															
Blood immunologic samples	X e	X e					X e		X f		X e		X e		X e	
HLA testing g									X							
Cervical cytology, ThinPrep™ h	X								X		X		X		X	
OP rinse, vaginal, and intra-anal swabs		X							X		X		X		X	
Cervical colposcopy	X														X	
Vulvoscopy i	X	X		X		X			X		X		X		X	
Vulvar lesion standardized photography j	X	X		X		X			X		X		X		X	
Biopsy k	X										X		X		X	
Vulvar HPV genotyping l	X										X		X		X	
Inject VGX-3100 +EP m		X		X		X		X				X m		X m		
Post treatment reaction assessment		X		X		X		X				X		X		
Dispense imiquimod + distribute imiquimod dosing log n		X		X		X										
Review imiquimod dosing log and usage				X		X		X								
Distribute Participant Diary (PD)		X		X		X		X				X		X		
Review PD o			X		X		X		X				X		X	
Adverse Events	X															X
Ultrasound Measure of skin-to-muscle and related thicknesses	X															
Patient Reported Outcomes (PROs) p		X	X	X	X	X	X	X	X		X	X	X		X	X

Abbreviations: OP; oropharynx

- a Full PE mandatory at screening and study discharge (Week 100), otherwise targeted PE as determined by the Investigator or per subject complaints unless signs or symptoms dictate the need for a full PE.

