- b Screening vital signs must include a measured height and weight and calculated BMI (Bodyweight in kilograms divided by height in meters squared). Weight will be measured at all dosing visits.
- c Screening 12-lead ECG, complete blood count (CBC), serum electrolytes, blood urea nitrogen (BUN), creatinine (Cr), glucose, ALT, CPK and urinalysis performed within 30 days prior to first dose administration.
- d Negative spot urine pregnancy test is required at screening and prior to each study treatment, vulvoscopy and biopsy/surgical excision.
- e At least 34 mL (4 x 8.5 mL yellow (ACD) tubes) whole blood and 4 mL serum per time point. At least 68 mL whole blood and 8 mL serum should be collected prior to first dose.
- f At least 51 mL [6 x 8.5 mL yellow (ACD) tubes] whole blood and 4 mL serum should be collected at Week 27.
- g HLA testing will be performed once from an existing PBMC sample.
- h HPV genotyping and Pap smears are performed on the same ThinPrep™ cervical specimen.
- i An additional visit may be scheduled to perform vulvoscopy if worsening of disease is suspected. Biopsies should not be performed at any visit other than at entry (Screening), Week 48, and Weeks 74 and 96 for Subgroups C and D unless the investigator suspects invasive cancer. All biopsy samples and/or excision samples must be sent to the PAC for review.
- j Standardized high resolution digital imaging of the vulva and the associated acetowhite stained lesion(s) must be performed prior to and after biopsy, and at all vulvoscopy examinations. Additionally, standardized high resolution digital imaging should be obtained during examinations of the vagina if lesions are identified, for documentation.
- k Tissue specimen and slides from all excised tissue must be reviewed by the PAC and residual vulvar tissue from entry, Week 48, 74 or Week 96 specimen(s) (paraffin blocks or unstained slides) should be sent to the central pathology laboratory for immunohistochemistry (IHC) and HPV testing.
- l HPV genotyping is performed on vulvar tissue specimen using a PCR based assay.
- m Potential dosing at Week 52 and Week 78 is applicable for partial responders only.
- n Subjects will take home imiquimod plus an imiquimod dosing log to document their use of imiquimod. Administration of imiquimod begins on Day 0.

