
6. Determine the efficacy of VGX-3100, alone or in combination with imiquimod, as measured by reduction in the surface area of vulvar lesion(s)
	
6. Percent reduction in the cumulative surface area of the acetowhite vulvar lesion(s) as determined by the quantitative analysis of standardized photographic imaging at Week 48, 74 and 96 compared to baseline. Results will be classified as: no clinically significant lesion resolution (reduction in lesion size of 0-25%), partial lesion area resolution (>25% and <100% reduction), and complete lesion resolution (no visible lesion).

7. Describe the humoral and cellular immune response of VGX-3100 administered alone or in combination with imiquimod, post dose 3, post dose 4, and after additional dosing
	
7a. Levels of serum anti-HPV-16 and anti-HPV-18 antibody concentrations at baseline, Weeks 15, 27, 48, 74, and 96 visits 7b. Interferon-<math>\gamma</math> ELISpot response magnitudes at baseline and Weeks 15, 27, 48, 74 and 96 visits 7c. Flow Cytometry response magnitudes at baseline and Week 27 visits

 Digital photos will be analyzed with a computer program to calculate the total lesion size in cm^2.

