## 2.3 EXPLORATORY OBJECTIVES AND ASSOCIATED ENDPOINTS

Exploratory Objectives	Associated Exploratory Endpoints
1. Describe the efficacy of VGX-3100, administered alone or in combination with imiquimod, at Week 74 and/or Week 96 as measured by reduction in the surface area of vulvar lesion(s), in subjects without a complete resolution at Week 48	1. Percent reduction in the cumulative surface area of the acetowhite vulvar lesion(s) as determined by the quantitative analysis of standardized photographic imaging at Week 74 and/or Week 96 compared to baseline  . Results will be classified as: no clinically significant lesion resolution (reduction in lesion area of 0-25%), partial lesion area resolution (>25% and <100% reduction), and complete lesion resolution (no visible lesion).
2. Describe the efficacy of 5 or 6 doses of VGX-3100, alone or in combination with prior imiquimod, as measured by histologic regression of vulvar HSIL	2. Proportion of subjects with no evidence of vulvar HSIL on histology (i.e. biopsies or excisional treatment) at Week 74 for subjects who receive 5 doses of VGX-3100 and at Week 96 for subjects who receive 6 doses of VGX-3100.
3. Describe the efficacy of 5 or 6 doses of VGX-3100, alone or in combination with prior imiquimod, as measured by virologic clearance of HPV-16/18	3. Proportion of subjects with no evidence of HPV-16/18 in vulvar tissue samples at Week 74 and/or Week 96.
4. Evaluate tissue immune responses to VGX-3100, and VGX-3100 with imiquimod, as measured in vulvar tissue samples	4. Assessment of CD8 + and FoxP3 infiltrating cells  .
5. Describe virologic clearance of HPV-16/18 from other anatomic locations outside the vulva	5. Proportion of subjects who have cleared HPV-16/18 on specimens from other anatomic locations without surgical intervention (inclusive of cervix, oropharynx, vagina and intra-anus) at Week 48
6. Characterize HLA haplotypes and the correlation with efficacy	6. Proportion of subjects with regression of HSIL on histology (i.e. biopsies or excisional treatment) at Week 48 visit
7. Assess skin-to-muscle, skin-to-bone, and muscle thicknesses via ultrasound measure of deltoid (or quadriceps if applicable) and the correlation of needle depth into muscle with efficacy.	7. Ultrasound-measured skin-to-muscle, skin-to-bone, and muscle thicknesses.

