### 3.2 EFFICACY ASSESSMENT

The efficacy assessment will be based upon histopathology. Visualization of a normal appearing vulva by visual inspection with vulvoscopy is insufficient evidence to confirm disease regression. Disease regression will be based on histopathologic assessment at Week 48, 74 and 96. Subjects will be monitored during the course of the study by vulvoscopy. Lesion(s), defined as areas that stain acetowhite, will be assessed during vulvoscopy at Screening, Day 0, and Weeks 4, 12, 27, 48, 74 and 96 visits. Using standardized high resolution digital imaging, vulvar lesion(s) will also be quantitatively measured at Screening, Day 0, and Weeks 4, 12, 27, 48, 74 and 96.

Biopsies obtained as part of the study at Screening will be from the region of most advanced and severe disease as judged by the Investigator, and must be a minimum of 4 mm in length. Visible lesion must remain after screening biopsy to ensure measurement on study.

The decision process following results of the Week 48 biopsy are described in [Figure 2](#) and are as follows: At Week 48, the subject will undergo repeat vulvar punch biopsy/biopsies of the same lesion as study start, but adjacent to the original site within the boundaries of the original lesion (see [Table 3](#) for Minimally Required Biopsy Procedures). If after evaluation of biopsy tissue by the PAC there is no evidence of HSIL ([Figure 2](#), Subgroups A or B), the subject will continue to Week 74 for vulvoscopy, and biopsy adjacent to the site of initial biopsy.

If after evaluation of the biopsy tissue HSIL remains, but there is a reduction in lesion size or no increase in lesion size from baseline ([Figure 2](#), Subgroups C or D), the Investigator has the option to give the subject a 5th dose of VGX-3100 at Week 52, and the subject will continue on study with vulvoscopy and biopsy at Week 74. Alternatively, the Investigator may choose to treat the subject with surgical or standard treatment, and the subject will continue on study without further biopsy.

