The decision process following results of the Week 74 biopsy are described in [Figure 3](#) and are as follows: At Week 74, the subject will undergo repeat vulvar punch biopsy/biopsies of the same lesion as study start, but adjacent to the original site within the boundaries of the original lesion (see [Table 3](#)). If after evaluation of biopsy tissue by the PAC there is no evidence of HSIL (Subgroups A or B), the subject will continue to Week 96 for vulvoscopy, and biopsy adjacent to the site of the initial biopsy.

If HSIL remains but there is a reduction in lesion size or no increase in lesion size from baseline (Subgroups C or D), the Investigator has the option to give the subject a 6th dose of VGX-3100 at Week 78, and the subject will continue on study with vulvoscopy and

biopsy at Week 96. Alternatively, the Investigator may choose to treat the subject with surgical or standard treatment, and the subject will continue on study without further biopsy.

The decision process following results of the Week 74 biopsy are as described in [Figure 4](#) and are as follows: At Week 96, the subject will undergo repeat vulvar punch biopsy/biopsies of the same lesion as study start, but adjacent to the original site within the boundaries of the original lesion (see [Table 3](#)). If there is no vulvar HSIL (Subgroups A or B), no further procedures are required. If after evaluation of biopsy tissue by the PAC there is vulvar HSIL (Subgroups C or D), or worsening disease (Subgroup E), the subject will receive surgical or other standard treatment.

In the event of worsening disease (ie, Subgroup E - any increase in lesion area from baseline or worsening of HSIL to cancer), the subject will receive surgical treatment per the Investigator's judgement and will continue on study through Week 100 with vulvoscopy, but without further biopsy. For a finding of carcinoma, subjects will receive surgical treatment, and be discontinued from study treatment. The event will be reported as an SAE per [section 7.1.4](#). If wide excision is required, the sample obtained will be sent to the PAC for evaluation.

Pre-biopsy Vulvoscopy Finding	Minimally required procedure
No acetowhite lesion	Vulvar punch biopsy and imaging; biopsy should be conducted of the same lesion as study entry, but adjacent to the original biopsy site within the boundaries of the original lesion;

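### Secondary endpoint 6 classes an absent lesion at Weeks 74 and 96 as complete resolution even when surgery has removed it

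*Protocol*

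**What the plan says.** The file holds protocol versions 1.0, 1.1 and 1.2. Version 1.2 is current but its text breaks off at section 6.12, so section 8 is cited from version 1.1.

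- Section 2.2, secondary endpoint 6 (and the synopsis): percent reduction in cumulative acetowhite lesion area at Weeks 48, 74 and 96 against baseline, in three classes. The top class is "and complete lesion resolution (no visible lesion").
- Section 2.3, exploratory endpoint 1: the same classes at Weeks 74 and/or 96, "in subjects without a complete resolution at Week 48".
- Section 3.2, Subgroups C and D, after the Week 48 result and again after the Week 74 result: as the alternative to a further dose, "the Investigator may choose to treat the subject with surgical or standard treatment, and the subject will continue on study without further biopsy".
- Section 3.2, Subgroup E, defined by "any increase in lesion area from baseline or worsening of HSIL to cancer": surgery per the investigator's judgement, after which the woman "will continue on study through Week 100 with vulvoscopy, but without further biopsy". The synopsis allows for this at any time in the study.
- Table 1: the row "Vulvar lesion standardized photography" is marked at Weeks 74 and 96 with no exemption for women who have had surgery. Footnote j says imaging "must be performed prior to and after biopsy, and at all vulvoscopy examinations".
- Section 2.3, exploratory endpoint 5, on HPV clearance outside the vulva, does carry a limit: "on specimens from other anatomic locations without surgical intervention".

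**The concern.** A lesion-area endpoint offered as evidence of drug efficacy should not improve because a surgeon removed the lesion. Here it can. The sharpest case is Subgroup E: a woman who enters it because her lesion grew, or became cancer, moves to the best class at the next imaging visit once she has been excised. Section 1.1.12 gives the overall aim as sparing women surgery or reducing it, so counting surgical clearance as success runs against the purpose of the trial. At stake are the Week 74 and Week 96 lesion-area results: the class percentages and the mean percent change.

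**Working it through.** No stated figure is in dispute. The check is whether any rule stops a post-surgery image from being classed as resolution, and then how much one case moves the result.

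**Does any rule stop it?**

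1. Is a post-surgery area recorded? Yes. For Subgroup E continued vulvoscopy is explicit, and footnote j attaches imaging to every vulvoscopy. For Subgroups C and D it follows from Table 1, which exempts nobody; section 3.2 stops only the biopsy.
2. Does the responder definition exclude it? No. Section 3.2.1, Table 4, names only non-study medication and concerns histology and virology, not lesion area.
3. Does the analysis text exclude it? Not in version 1.1. Section 8.4 keeps every dosed woman who has the endpoint, section 8.9 gives the mean percent change and class percentages with no surgery rule, and section 8.11.6 works from reported values.

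**Which visits are exposed?** Footnote j, and section 6.14 in version 1.1, require images before as well as after a procedure. Taking the pre-procedure image as the one measured:

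| Time of surgery | Lesion-area visits affected |
|---|---|
| Before Week 48 (Subgroup E) | 48, 74, 96 |
| At Week 48, or after it and before Week 74 | 74, 96 |
| At Week 74, or after it and before Week 96 | 96 |
| At Week 96 | none |

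**Size per woman.** Section 8.3 (version 1.1) gives 36 women randomized 2:1, hence 24 and 12, with 90% evaluable at Week 48.

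- Evaluable: 0.9 × 24 = 21.6, about 22; 0.9 × 12 = 10.8, about 11. These are Week 48 figures; if fewer women are imaged at Weeks 74 and 96, each counts for more.
- Addition to the complete-resolution percentage per fully cleared woman: 100/22 = 4.5 points; 100/11 = 9.1 points.
- Two such women among 11, with no drug response at all: 2/11 = 18.2%, Clopper-Pearson 95% CI 2.3% to 51.8%.
- Rise in mean percent reduction per cleared woman: (100 − r)/n, where r is her percent reduction just before surgery. The r values are assumed:

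| r | n = 22 | n = 11 |
|---|---|---|
| 50 (halved) | 50/22 = 2.3 | 50/11 = 4.5 |
| 0 (unchanged) | 100/22 = 4.5 | 100/11 = 9.1 |
| −25 (grown by a quarter) | 125/22 = 5.7 | 125/11 = 11.4 |

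**The case against.** The strongest reply is that handling of post-surgery observations belongs in the SAP, which is not shown, and that no sentence says surgical cases will be counted as responses. It stands in part: a SAP could add a rule, and section 8 of version 1.2 cannot be read here. But the protocol itself fixes the variable and its classes, and a SAP that reclassified these women would depart from that definition. The protocol also places such a limit inside an endpoint when it wants one, in exploratory endpoint 5.

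A second reply concerns exploratory endpoint 1. Because it is confined to women not resolved at Week 48, a reader might infer that it is the worse affected of the two. Section 8.1 (version 1.1), however, describes the exploratory analysis of anatomic extent as concerning extended dosing. Under section 3.2 surgery is the alternative to the extra dose, so on that reading women operated on instead of receiving dose 5 fall outside it. What remains is surgery after dose 5 and before a later imaging visit. The endpoint's own wording does not require an extra dose, so the gap is there, but the exposure is smaller.

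Third, the consequence is limited. Section 8.9 (version 1.1) gives secondary binary endpoints no p-values, and exploratory endpoint 1 is descriptive. That is correct.

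Fourth, neither a surgery rate nor a post-surgery clearance rate over these intervals is given. The recurrence figures in sections 1.1.4 and 1.1.5 do not supply one: the former has no time frame and the latter refers to three years. That is also correct, and is why the size is given per woman only.

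**Conclusion.** The point holds for secondary endpoint 6 at Weeks 74 and 96, and with less exposure for exploratory endpoint 1. Applied as written, the definition counts surgical removal as VGX-3100 efficacy, by up to 4.5 points (about 22 evaluable) or 9.1 points (about 11) of complete resolution per fully cleared woman. This rests on the 90% evaluable assumption made for Week 48 and, for Subgroups C and D, on Table 1 being followed after surgery. The total distortion cannot be stated because the number of such women is unknown.

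A reader might infer that the trial's efficacy conclusion is compromised. The documents do not support that: the primary endpoint rests on Week 48 histology and virology and does not use lesion area. Nor is the Week 48 area generally at risk; only surgery before that visit can affect it. The change is worth making before the Week 74 and 96 data are summarized.

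**What to change.** Add to the definitions of secondary endpoint 6 and exploratory endpoint 1, and mirror in the synopsis:

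*Complete or partial resolution requires that vulvar lesions have had no prior surgical or other non-study treatment. At visits after such treatment the woman is classed as not resolved and her post-treatment area is not used in the mean percent change. The number so treated is reported by arm and visit.*

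Add a sensitivity summary using the last area photographed before treatment. Carry-forward should not be the main rule: it freezes the cumulative area, so it can hide later growth of other lesions or a recurrence and can flatter the result. Placing the rule in the definition also avoids a clash with the no-imputation rule in section 8.11.6 (version 1.1).

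The cost is wording only. It needs no new visit or procedure and does not limit the investigator's freedom to operate. The downside is slightly lower Week 74 and 96 resolution percentages and fewer women in the mean percent change. Those left out of the mean may be the poorer responders, which the sensitivity summary would help to show.
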